## 2021-P-000961 Detailed Protocol

### I. BACKGROUND AND SIGNIFICANCE

This project is designed to test for the first time whether glucose metabolism is differentially impaired by sleep restriction with and without additional exposure to artificial light at night (ALAN). Laboratory studies have shown that sleep restriction to 4-6h per night for durations varying from one to 14 days reduces glucose tolerance in otherwise healthy adults [10-23,32,33], but the mechanisms by which insufficient sleep impairs glucose metabolism are still unknown. Current theories are based on the premise that the adverse metabolic consequences are caused by reduction in the duration of sleep *per se* [34]. However, sleep curtailment is typically accompanied by longer exposure to artificial light at night (ALAN), which is an environmental endocrine disrupter that profoundly disrupts circadian rhythms [24-27,35-37].

We have previously reported that acute circadian misalignment induced hyperglycemia comparable to pre-diabetic states in a third of otherwise healthy participants [55]. Since then, we have shown that even when the circadian phase of participants was realigned, prior exposure to 2 ½ weeks of chronic sleep restriction combined with a history of recurrent circadian disruption induced even more deleterious effects on glucose metabolism [32], in which pancreatic beta cells failed to respond adequately to increased glucose levels. Moreover, both night and rotating shift work (which induce circadian disruption) are associated with increased risk for metabolic problems (81)(82)(83)(84)(85)(86)(87). Night shifts can lead to acute increases in glucose and insulin levels (88), although some studies report reduced insulin release in response to meals consumed during the night (89-91). Given that circadian disruption has been shown to independently adversely affect metabolism, and exposure to ALAN adversely impacts metabolism in animals [38], it is important to understand the extent to which circadian disruption contributes to the observed impact of sleep curtailment on metabolism[35]. **No previous studies of the metabolic impact of sleep restriction in humans have controlled for this additional exposure to ALAN, thus confounding the effects of sleep restriction with the effects of circadian disruption caused by extended exposure to ALAN.**

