## II. SPECIFIC AIMS

The goal of this project is to evaluate whether extended duration ALAN contributes to the adverse effects of sleep restriction on glucose metabolism. We plan to use a crossover design consisting of a 7-day baseline, 7-day sleep restriction (to 5h per night) with (LD 19:5) or without (LD 14:10) ALAN, 9-day washout, and another 7-day sleep restriction with or without ALAN (Figure 8). 20 healthy participants will be randomly assigned to receive ALAN in either the first or second exposure, balanced by age and sex. Specifically, we plan to:

1. Test the hypothesis that exposure to one week of sleep restriction with concurrent exposure to extended duration ALAN (LD 19:5) will induce greater impairment of insulin sensitivity than exposure to one week of sleep restriction without extended duration ALAN (LD 14:10). Insulin sensitivity (SI) will be assessed via an intravenous glucose tolerance test (ivGTT) before and after each week of exposure.
2. Test the hypothesis that exposure to one week of sleep restriction with concurrent exposure to extended duration ALAN (LD 19:5) will induce greater impairment of glucose tolerance than exposure to one week of sleep restriction without extended duration ALAN (LD 14:10). The 90-minute glucose area under the curve (AUC) will be assessed in response to a standardized meal both before and after each week of exposure.
3. Test the hypothesis that exposure to one week of sleep restriction with concurrent exposure to extended duration ALAN (LD 19:5) will reduce the duration of nocturnal melatonin secretion as compared to baseline more than exposure to one week of sleep restriction without extended duration ALAN (LD 14:10). The 24-h profile of melatonin secretion will be assessed during the lighting conditions that prevail throughout both sleep restriction conditions (i.e., 5h in darkness per night vs. 10h in darkness/near darkness per night). To determine the mechanism of this anticipated decrease in the duration of melatonin secretion (acute light-induced melatonin suppression vs. a reduction in the duration of the endogenous melatonin secretory profile), we will also measure the endogenous melatonin secretory profile on a ~24-hr recording on the day immediately after each week of intervention.

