## **IV. SUBJECT ENROLLMENT**

This study uses a within-subjects randomized crossover design to compare the effects of sleep restriction with and without ALAN on glucose metabolism. The order in which subjects undergo the two sleep interventions will be randomized.

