For the **Washout**, sleep episodes will be scheduled to 10 hours each night at the same time of the Baseline sleep episodes, from Days 15-23. Upon awakening after an overnight fast toward the end of the Washout (~Day 23), the participant will undergo the second **Baseline** assessment of their resting metabolic rate, glucose and insulin responses, and melatonin rhythms. Standardized Mixed Meal Responses, ivGTTs, and melatonin sampling will be carried out on the next 3 days (~Days 23-25) as performed during the first Baseline assessment on Days 6-8. Following the washout, the next 7 nights are the **Second Sleep Intervention**, during which participants will undergo the sleep restriction condition (with or without ALAN) which they have not yet undergone during the first sleep intervention.

Upon awakening after an overnight fast at the end of the 7-day exposure (~Day 31), the participant will undergo another re-assessment of their resting metabolic rate, glucose and insulin responses, and melatonin rhythms. Standardized Mixed Meal Responses, ivGTTs, and melatonin sampling will be carried out on the next 3 days (~Days 31-33) as performed during the assessment following the first Sleep Intervention on Days 14-16. The final **Recovery** sleep episode on Night 32 will be scheduled for 10 hours at the same time of the Baseline sleep episodes. Blood sampling will be completed approximately 10 hours after waketime on Day 33, at which time the sampling IV will be removed and the participant will be discharged. At the times indicated above when blood sampling is scheduled, we may collect additional small amounts of blood to assay for proteins, lipids, transcripts, or metabolites.

**How Biospecimens, Data, and/or Records, will be Obtained.** As outlined above, activity/light data and diary recordings, as well as a blood sample for DNA extraction will be collected from participants during the pre-study screening period. In the laboratory study, PSG sleep and wake recordings, answers to written and computerized questionnaires, whole blood and saliva biospecimen will be collected. We may also collect breath samples and fecal samples during specific days of the study.

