## VI. Biostatistical analysis

Intent-to-treat analysis and per protocol analysis will both be performed. The amount and patterns of missing data, if any, will be characterized. We will use all available data points in the mixed-effects model. The study will be monitored routinely for issues of data quality, study conduct, and adverse events. We do not plan to do interim analysis. Mediation analysis will be performed to study the relationship between extended-duration ALAN exposure, duration of melatonin secretion, and the primary outcomes (insulin sensitivity and glucose tolerance). Paired t-test (or Wilcoxon signed-rank test) will be used to compare the change from baseline in insulin sensitivity (SI), acute insulin response (AIRg), glucose effectiveness, glucose AUC, insulin AUC, and the duration of the melatonin profile after exposure to sleep restriction with and without ALAN. Linear mixed models will also be used to compare the change in these outcomes from baseline to after exposure to sleep restriction with and

without ALAN in case of missing data and with potential covariates, such as age and sex.

*Insulin sensitivity (SI) (Specific Aim 1).* An insulin-modified IVGTT will be carried out on Days 4 and 11 after an overnight fast [13]. Blood samples will include pre-test baseline samples. At time 0 (time of usual breakfast), 0.3 g/kg glucose will be administered over 1 minute. Blood samples will be taken every minute for the initial 6 minutes, every ~2 minutes for the following ~20 minutes. At time +20 min, 0.02U/kg human insulin will be administered intravenously over 1 minute. Blood samples will continue to be taken every 5 minutes for the following half hour, every 10 minutes for the next ~half hour, and every 20 minutes for the next 1.5 hours. Minimal Model Analysis 3 will be used to assess insulin sensitivity (SI).

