### Sample size and power calculation

We will consider three primary outcomes: insulin sensitivity for Specific Aim 1; glucose AUC for Specific Aim 2; and duration of melatonin secretion for Specific Aim 3. Sample size and power calculations are based on results from our previous studies. In the study of one week of sleep restriction to 5 h/night[13], we observed a ~28% decrease in insulin sensitivity as assessed by ivGTT. We anticipate a similar effect on insulin sensitivity in participants assigned to the Sleep Restriction with extended duration Artificial Light At Night (ALAN) group in the proposed study, given the identical conditions of 1 week of sleep restriction. In a separate study, no impairment of glucose tolerance was observed in a group of participants exposed to sleep restriction without extended duration exposure to ALAN (See Preliminary Studies, Fig. 3). With 20 subjects, we have 83% power ( $\alpha=0.05/3=0.0167$ , 2-sided paired t-test) to detect as little as a 13% difference between the conditions in the change from baseline (18% change with ALAN vs. 5% change without ALAN) in insulin sensitivity (assuming the common standard deviation (SD) of the change is 16%). This should be more than adequate to detect the difference in insulin sensitivity we expect to observe in the proposed study. For Specific Aim 2, with 20 subjects, we estimate that we have 83% power ( $\alpha=0.0167$ , 2-sided paired t-test) to detect as little as a 3.65% difference between the conditions in the change of glucose AUC (assuming common SD= 4.5%). This should be more than adequate to detect the difference in glucose AUC we expect to observe, given that we have previously observed an over 20% change in glucose AUC following a prior history of recurrent circadian disruption combined with chronic sleep restriction[32].

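### The crossover's primary tests name no period or sequence term; adding one is a cheap safeguard at the minimum detectable differences, not a correction of a wrong figure

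*Combined protocol and SAP*

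**What the plan says.** Section IV fixes the design: "The order in which subjects undergo the two sleep interventions will be randomized". Under Specific Aims, insulin sensitivity is "assessed via an intravenous glucose tolerance test (ivGTT) before and after each week of exposure". Section V schedules a washout with 10-hour nights and then a second baseline: "ivGTTs, and melatonin sampling will be carried out on the next 3 days (~Days 23-25) as performed during the first Baseline assessment". Each period therefore has its own baseline and post-exposure value.

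Section VI gives the analysis: "Paired t-test (or Wilcoxon signed-rank test) will be used to compare the change from baseline in insulin sensitivity (SI", together with the other metabolic and melatonin outcomes, between the two conditions. Linear mixed models on the same changes are to be used for sleep restriction with and "without ALAN in case of missing data and with potential covariates, such as age and sex". Neither Section VI nor the power section mentions period, sequence or order. The words introducing age and sex leave the covariate list open, so period is unspecified rather than excluded.

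The power section sizes the trial for an unadjusted two-sided paired t-test at alpha 0.0167 with 20 subjects, "to detect as little as a 13% difference between the conditions in the change from baseline" for insulin sensitivity. Section III expects that up to 25 may be enrolled to obtain 20 completers. No rule keeps completers equal between the two sequences.

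**The concern.** In a two-period crossover, the within-person ALAN minus no-ALAN difference contains the treatment effect plus or minus any period difference, with the sign set by sequence. A paired test ignores sequence. A period difference therefore inflates its error term and, when completers are unequal, shifts its estimate. Age and sex are constant within a person, so as main effects they cannot remove this.

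Separate baselines deal with one form of the problem: a shift in level common to a period's baseline and post value cancels. What does not cancel is a period difference in the response to sleep restriction. Everyone enters period 2, but not period 1, with a week of 5-hour nights behind them. The Background gives a reason not to take the difference as zero: it reports that earlier chronic sleep restriction with "a history of recurrent circadian disruption induced even more deleterious effects on glucose metabolism", even after circadian phase had been realigned.

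At stake is power at the minimum detectable differences, where n is fixed at 20 and stated power is 83 to 84%, and, for a given unequal split, the estimate itself.

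**Working it through.** **Inputs from the power section.** n = 20; two-sided alpha = 0.05/3 = 0.0167. Difference and SD: insulin sensitivity (SI) 13 and 16 points; glucose AUC 3.65 and 4.5 points; melatonin duration 40 min (also given as 0.66 h) and 48 min. Each SD is taken as the SD of the within-person difference of changes, because that reading reproduces the stated power.

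**Assumed.** P, the period 1 minus period 2 difference in the change. The documents give no value.

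**1. The plan's own figures.** Noncentral t, 19 df, noncentrality (difference/SD) × √20. For SI, (13/16) × 4.472 = 3.634, giving 83.2% (stated 83%). AUC: 83.0% (stated 83%). Melatonin: 85.2% at 40 min, 84.4% at 0.66 h (stated 84%).

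**2. Model.** Let d be a person's change under ALAN minus change under no ALAN, and s = +1 if ALAN came first, −1 if second. Then d = δ + P·s + error.

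- Paired test: the mean of d has expectation δ + P(n1 − n2)/20, and its sample SD also absorbs P.
- With the term: regress d on s. The intercept is the mean of the two sequence means, with SE = (SD/2)·√(1/n1 + 1/n2) on 18 df, and does not depend on P.

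**3. Cost when P = 0.** At 10:10 the SI SE is 8 × √0.2 = 3.578, noncentrality 3.634 on 18 df, power 82.8%. At 11:9, 12:8 and 13:7 it is 82.3, 81.0 and 78.6%. AUC and melatonin (40 min) at 10:10 are 82.6 and 84.8%.

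**4. Power of the paired t-test at 10:10 when P is not zero** (simulation; results agree to within about 0.2 points between runs).

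| Outcome | P | Paired t | With term |
|---|---|---|---|
| SI | 5 / 8 / 10 points | 79.9 / 74.4 / 69.0% | about 82.8% |
| AUC | 1.4 / 2.25 / 2.8 points | 79.7 / 74.2 / 69.0% | 82.6% |
| Melatonin | 15 / 24 / 30 min | 82.1 / 77.0 / 72.0% | 84.8% |

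For SI the two tests break even at about 2 points. At 3 points the paired test still has about 82%. For the Wilcoxon option, signed-rank power for SI is 80.9, 77.0, 71.5 and 65.4% at 0, 5, 8 and 10 points, against about 79% throughout for a rank-sum test between sequences.

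**5. Unequal completers.** If 13:12 enrol (an assumption) and 5 are lost at random, the hypergeometric split is 10:10 in 36%, 11:9 in 48%, 12:8 in 15% and 13:7 in 1.5%. The shift in the paired estimate is P(n1 − n2)/20, that is 0.1, 0.2 and 0.3 of P at the unequal splits. At P = 8 for SI:

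| Split | Shift (points) | Paired power, shift opposes / inflates effect | With term | Paired type I error |
|---|---|---|---|---|
| 11:9 | 0.8 | 67.5 / 80.4% | 82.3% | 0.009 |
| 12:8 | 1.6 | 60.2 / 85.8% | 81.0% | 0.014 |
| 13:7 | 2.4 | 52.9 / 90.0% | 78.6% | 0.022 |

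At 10:10 and P = 8 the paired type I error is 0.008. With the term it stays at 0.016 to 0.017 and the shift is zero. Averaged over these splits with P = 0, power with the term is 82.2% against 83.2%, and break-even lies between 2 and 3 points.

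**6. At the effect the sponsor expects.** Taking 28% with ALAN and an assumed 5% without, δ = 28 − 5 = 23 points. The paired t-test still has about 99.7% power at a 13-point period difference.

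**The case against.** The strongest reply is that nothing in the plan is shown to be wrong. The paired test is valid, its stated power is right on the reading of the SD used here, and the covariate list is open. The benefit rests on a quantity that the documents do not supply; 8 points is more than 60% of the 13-point target (8/13 = 0.62), and at 3 points or less the loss is about 1 point. The sponsor expects effects well above those powered: about a 28% fall in SI with ALAN, and a melatonin difference of more than 3 hours against 40 minutes. All of that stands, and it limits the point to a safeguard.

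It also stands that one degree of freedom understates the cost when splits are unequal, and that the shift is conditional on the realised split: if either sequence is equally likely to be the larger, the paired estimate is unbiased on average. Two stronger readings fail:

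- *The false-positive rate is inflated.* Under the assumptions above, type I error is at or below nominal except at 13:7, a split with 1.5% probability.
- *The Background shows that the washout fails.* The earlier study combined about two and a half weeks of restriction with recurrent circadian disruption. It did not test recovery over a washout such as this one, where "sleep episodes will be scheduled to 10 hours each night at the same time of the Baseline sleep episodes, from Days 15-23".

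What the reply does not remove is that the named test, followed as written, leaves any period difference in response in its error term, when a standard alternative at almost no cost takes it out.

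**Conclusion.** The point holds as an improvement to the analysis, not as an error in a stated figure. If the response to sleep restriction differs between periods by 5 to 10 points on SI, the paired t-test has 79.9 down to 69.0% power at the minimum detectable difference with 10:10 completers, against about 82.8% with the term. For a given unequal split the term also removes a shift of 0.1 to 0.3 of the period difference. Below about 2 points (2 to 3 averaged over splits) the term gains nothing, and at the expected effects the gain is close to nil.

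This rests on an assumed period difference in response, on random losses from 13:12, and on 16% being the SD of the within-person difference. If it were instead each condition's SD with uncorrelated changes, the SD of the difference would be 16 × √2 = 22.6 and baseline power 49%.

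A reader might infer that a period term would also protect against carryover. It does not correct a residual effect left only by having ALAN first.

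**What to change.** For each primary outcome, pre-specify as primary the within-person ALAN minus no-ALAN difference in change from the period's own baseline, regressed on a sequence indicator coded +1/−1. The intercept is the ALAN effect (18 df at n = 20). Use the scales that were powered: percent change for SI and AUC, minutes for melatonin. If a rank test is needed, compare the two sequences by rank-sum test on the period 1 minus period 2 change.

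In the mixed model on change, name condition, period and random subject; age and sex may stay. Keep this model for the intent-to-treat analysis of all available data, so that participants with only one period contribute. In complete data its ALAN estimate equals the regression intercept. Its standard error can be up to 21% smaller when the subject variance is estimated as zero, so the regression should carry the primary test. Retain the paired t-test or Wilcoxon test as a sensitivity analysis.

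The change is to the wording of Section VI; no new data are needed. With no period effect, SI power goes from 83.2% to 82.8% at 10:10, 82.3% at 11:9, 81.0% at 12:8 and 78.6% at 13:7. The wording should be settled before outcome data are seen, since choosing the term afterwards would invite selective analysis.

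### The primary paired test fixes the weight of each period's baseline at 1 and no baseline covariate is pre-specified; fitting that weight is a cheap but assumption-dependent gain in precision

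*Combined protocol and SAP*

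**What the plan says.** Section II (Specific Aims) says that insulin sensitivity "will be assessed via an intravenous glucose tolerance test (ivGTT) before and after each week of exposure", and the mixed-meal glucose response follows the same before-and-after pattern. Section V (Study Procedures) repeats the full baseline after the washout: "Standardized Mixed Meal Responses, ivGTTs, and melatonin sampling will be carried out on the next 3 days (~Days 23-25"). Each completer therefore has four values of insulin sensitivity and of glucose AUC: a baseline and a post-exposure value in each of two periods. Melatonin is sampled on the same occasions.

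Section VI names the main comparison: "Paired t-test (or Wilcoxon signed-rank test) will be used to compare the change from baseline in insulin sensitivity (SI") and the remaining outcomes, with ALAN set against no ALAN. The sample size section powers all three primary outcomes on a two-sided paired t-test at 0.05/3.

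Section VI also plans a second analysis, again on change: "Linear mixed models will also be used to compare the change in these outcomes from baseline to after exposure to sleep restriction" under the two lighting conditions. Its purpose is to handle missing values and to allow adjustment, and age and sex are given as examples of what may be adjusted for. On the data to be used, the section says: "We will use all available data points in the mixed-effects model". Baseline is not named as a covariate in either analysis.

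**The concern.** In a crossover, the ALAN versus no-ALAN comparison within a person already cancels that person's stable level. The own-period baseline can then help only by tracking how the person drifted between periods. Subtracting it in full assumes that all of a between-period baseline difference carries through to the post-exposure value. If only part of it does, the rest enters the contrast as extra variation.

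The named covariates do not help here. Age and sex are constant within a person, so their main effects drop out of the contrast in complete pairs. The one measured quantity that varies within a person and could explain variation, the own-period baseline, has no pre-specified role as a covariate.

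What is at stake is precision. Each completer costs a 33-day inpatient stay with two weeks of sleep restriction, and up to 25 people may enter the main study to obtain 20 completers (section III). The open covariate list matters too: adding baseline after the data are seen would be a data-dependent choice.

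**Working it through.** **Inputs from the sample size section.** n = 20; alpha = 0.05/3 = 0.0167, two-sided; insulin sensitivity difference 13 points, SD 16; glucose AUC 3.65, SD 4.5; melatonin duration 0.66 h (39.6 min), SD 48 min.

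**1. Reproduce the plan's power.** For a paired t-test with 19 df, the noncentrality is (difference/SD) × √20. For insulin sensitivity this is (13/16) × 4.472 = 3.63, which gives 83.2% (stated 83%). Glucose AUC gives 83.0% (stated 83%) and melatonin 84.4% (stated 84%). These match when the stated SD is used as the SD of the paired difference between the two changes; I keep that reading.

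**2. Compare the two estimators.** For each participant let P be the ALAN minus no-ALAN difference in post-exposure values and B the same difference in baselines. The planned test uses P − B. The alternative regresses P on B and tests the intercept. With β the least-squares slope,

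Var(P − B) = Var(P − βB) + (1 − β)² Var(B).

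In large samples a fixed weight of 1 therefore cannot beat the fitted weight. If P and B have equal variance V and correlation r, then Var(P − B) = 2V(1 − r), Var(P − rB) = V(1 − r²), and the ratio is (1 + r)/2.

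**3. Charge for estimating the slope.** At n = 20 this inflates the variance by about 1 + 1/(20 − 3) = 18/17, and leaves 18 df.

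**4. Results**, with the SD of P − B held at the plan's 16. The documents give no r, so it is assumed.

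| r | (1 + r)/2 | × 18/17 | variance saved | insulin sensitivity power |
|---|---|---|---|---|
| 0 | 0.50 | 0.529 | 47% | 98.5% |
| 0.2 | 0.60 | 0.635 | 36% | 96% |
| 0.5 | 0.75 | 0.794 | 21% | 91% |
| 0.8 | 0.90 | 0.953 | 5% | 85% |
| 0.9 | 0.95 | 1.006 | −1% | 82.5% |
| 0.95 | 0.975 | 1.032 | −3% | 81% |

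Worked line for r = 0.5: SD = 16 × √0.794 = 14.26; noncentrality = (13/14.26) × 4.472 = 4.08; power 91%. This matches the precision of about 20/0.794 = 25 completers analysed by change.

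Simulation (40,000 runs per r) gave 98.5%, 96.1%, 91.1%, 85.1% and 82.6% for r = 0, 0.2, 0.5, 0.8 and 0.9, with type I error near 0.0167. Repeating it with a period term as well (17 df, 10 participants per order) gave about 98%, 91% and 84% at r = 0, 0.5 and 0.8.

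**5. Unequal variances.** If B has only 0.7 times the SD of P, adjustment loses about 1-3 power points at r = 0.5 to 0.8. If B has 1.3 times the SD of P, simulated power is at least 96%.

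**6. Carryover.** Assume a 6-point residual effect in the second period for participants who had ALAN first. Half the sample is affected, so the mean shift is 3 points.

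- In both second-period tests: the shift cancels in P − B (bias 0). Adjustment leaves −3(1 − β), which is −3 at β = 0, −1.5 at 0.5 and −0.6 at 0.8.
- In the second baseline only: change is biased by +3. Adjustment is biased by 3β, which is 0, +1.5 and +2.4.

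**The case against.** The strongest reply is that nothing is broken. The change contrast is valid, the aims are framed as before-and-after comparisons, and the power was calculated for this same test and reproduces. All of that stands. A reader might infer that the choice leaves the trial underpowered; on the plan's own assumptions it does not.

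A reader might also infer that the plan discards a known share of its precision, say 10-50%. That range is (1 − r)/2 for r between 0.8 and 0. The documents give neither r nor any test-retest error, the cost of the slope lowers the range to about 5-47% at n = 20, and the gain disappears near r = 0.9. r may also differ between the three outcomes, so one verdict for all of them is not supported.

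Nor do the documents exclude baseline as a covariate. The covariate list is introduced by example, and the mixed model is to use all available data. Baseline adjustment is unspecified. Where a period is missing, age and sex need not cancel as they do in complete pairs.

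It is tempting to add that adjustment protects against an incomplete washout. Step 6 shows that this holds only if the residue affects the second baseline and not the second post-exposure test. If it affects both equally, subtraction is the safer choice.

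Finally, the 83% refers to the smallest targeted difference. If ALAN lowers insulin sensitivity by the 28% seen previously, against the plan's 5% without ALAN, the difference is 23 points and change-score power already exceeds 99.9%. The gain matters most if the true effect is near the 13-point target.

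**Conclusion.** The point holds as an efficiency improvement. The primary test fixes the baseline weight at 1, no baseline covariate is pre-specified, and the named covariates add no precision to the within-person contrast in complete pairs. Fitting the weight would save about 47%, 21% and 5% of the variance at r = 0, 0.5 and 0.8, and raise insulin sensitivity power from 83% to about 98%, 91% and 85%. At r of about 0.9 or above there is no gain, or a loss of 1-2 power points. A small loss is also possible when baseline differences vary less than post-exposure differences.

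These figures rest on an assumed r, equal variances of the baseline and post-exposure differences, approximate normality, 20 complete pairs and no carryover. They also treat the plan's percentage figures as points on an additive scale. The planned analysis is not invalid, and its stated power is correct for the test it names.

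**What to change.** In section VI, pre-specify as the primary analysis of each primary outcome a linear mixed model of the post-exposure value. Its terms would be condition, period, own-period baseline (centred within person), the person's mean baseline and a random participant effect. For complete pairs this amounts to regressing the ALAN minus no-ALAN post-exposure difference on the matching baseline difference, with an adjustment for order. State the scale of analysis for each outcome; for outcomes planned in per cent, a log scale is the additive counterpart. Keep the paired t-test or signed-rank test on change as a sensitivity analysis. Settle the wording before any outcome data are compared by condition.

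The cost is a change of text and no new data. The baseline slope takes one degree of freedom and the period term another. There is a small loss of power if r is very high. The primary analysis also gives up the change score's cancellation of carryover that affects both second-period tests equally, which is a reason to report the change analysis beside it. The text should not claim that adjustment always reduces the effect of an incomplete washout.
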